9.7. Exposure and Dose Reduction/Interruption

Dose reduction/interruption due to AE and other reasons will be summarized. A dose reduction is defined as any non-zero reduced dose of lenalidomide with AE or any other reason recorded on the eCRF page "Study Drug Record". Dose interruption is defined as any zero dose of lenalidomide with AE or any other reason recorded on the eCRF.

If an interruption happens at the start of a cycle and causes the cycle to be delayed, it is also called a dose delay. A maximum delay of 2 weeks in the start of cycle will be allowed. For example subjects treated with lenalidomide at Cycle 1 should start the second cycle of treatment no later than 42 days after cycle Day 1 of Cycle 1. Dose delays will be considered together with dose interruptions.

Dose Interruption Criteria:

- Lenalidomide will be held for any subject experiencing hemorrhagic or bullous skin rash until a specific evaluation to exclude toxic epidermal necrolysis and/or Stevens-Johnson syndrome has been performed. Any subject with evidence of toxic epidermal necrolysis or Stevens-Johnson syndrome will not be retreated with lenalidomide.
- Guidelines for GVHD as reported in the protocol section 8.2.1 in “Special Instructions for Management of Graft Versus Host Disease (GVHD)” paragraph.

Dose Reduction:

- Two dose reductions will be allowed (Table 2) in the event of specific protocol-defined toxicity. If treatment is interrupted for toxicity as described below, lenalidomide will be resumed at dose level -1 once the toxicity has resolved to \leq Grade 1. If toxicity recurs, lenalidomide will be interrupted and upon resolution, the subject will resume at dose level -2.
- The dose will not be re-escalated if the lower dose is tolerated.
- Subjects who do not tolerate 1 mg/kg/day (dose level -2) will discontinue lenalidomide administration.

Table 2: Dose Reductions of Lenalidomide

Dose Level	Dose
Starting dose	2.0 mg/kg/day (maximum dose of 70 mg/day for subjects \geq 35 kg)
Dose Level -1	1.4 mg/kg/day (not exceeding 50 mg/day for subjects initially dosed at 70 mg/day)
Dose Level -2	1.0 mg/kg/day (not exceeding 35 mg/day for subjects initially dosed at 70 mg/day)

The total number of cycles received and the overall number of dose reductions/interruptions for lenalidomide will be presented. The overall number and percentage of subjects who have at least one dose reduction/interruption for lenalidomide will be provided for each reason. Time to first dose reduction/interruption due to any reason will be descriptively provided. Time to first dose reduction/interruption due to AE will also be descriptively provided. Computation of similar summary statistics and frequency counts will be repeated by cycle and presented in a separated table.

The cycle when the dose reduction/interruption due to AE for lenalidomide, defined as the cycle number during which the dose of lenalidomide was reduced/interrupted due to AE, will be summarized as frequencies within the 4 categories: 1, 2, 3, and >3 cycle.

9.8. Overdose

Overdose, as defined in the protocol, refers to lenalidomide dosing. On a per dose basis, an overdose is defined as the following amount over the protocol-specified dose of lenalidomide assigned to a given subject, regardless of any associated AEs or sequelae: >10% over the protocol-specified dose.

On a schedule or frequency basis, an overdose is defined as anything more frequent than the protocol-required schedule or frequency.

Complete data about any overdose, regardless of whether the overdose was accidental or intentional, will be collected on the eCRF page "Investigational Drug Overdose" and will be presented in a listing.

10. EFFICACY ANALYSIS

Efficacy analyses for the primary endpoints will be performed on the RR and ITT population. Secondary efficacy endpoints will be analyzed for the ITT population.

Data listings will be provided for all endpoints, including bone marrow sample collection and assessment. Moreover bone marrow assessment performed at screening for diagnosis confirmation will also be listed.

10.1. Analysis of Primary Efficacy Endpoint

The primary endpoint is the morphological complete response rate within a maximum of 4 cycles of treatment. Morphological complete response is defined as CR or CRi as assessed locally and reported in the "Modified IWG Response Assessment" eCRF page. These response criteria will be assessed according to the revised AML IWG Criteria (Cheson, 2003, see Section 18.1).

The morphological complete response rate is defined as the total number of subjects with morphological complete response observed within the first 4 cycles of study therapy (regardless of whether the CR/CRi is observed at the end of Cycle 1, 2, 3 or 4) over the total number of subjects evaluable for this endpoint. The CR/CRi does not need to be present at the end of Cycle 4 if observed before this time for the subject to be considered as having achieved a complete response with regards to the primary endpoint. Responses occurring after a treatment failure assessment outcome will not be considered. The corresponding Clopper Pearson 95% confidence interval will be calculated for the response rate.

The primary analysis of this endpoint will be based upon the ITT population and the RR population.

Data as collected in the "Modified IWG Response Assessment" eCRF page will be listed.

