- ^r BMA/biopsy and peripheral blood smear must be collected at the completion of the 21-day treatment period within 6 days **before dosing for the subsequent cycle** (ie, between Day 22 to Day 27 of that cycle) in Cycles 1, 2, 3 and 4. If morphologic CR/CRi is achieved within the first 2 cycles, the BMA/biopsy and peripheral blood smear will not be required at the end of Cycle 3. These assessments are required for all subjects at the end of Cycle 4, and at the Treatment Discontinuation Visit or at the time of suspected relapse (whichever occurs first). An IWG response assessment will be performed whenever a bone marrow assessment is performed.
- ^s For subjects who are assessed as having partial response, the BMA/biopsy and peripheral blood smear will be repeated at Cycle 8 **unless** the subject goes to allogeneic HSCT, and at the Treatment Discontinuation Visit or at the time of suspected treatment failure (whichever occurs first).
- ^t During the study, repeat of bone marrow local cytogenetic/FISH testing is to be completed whenever a bone marrow aspirate/biopsy is obtained. However, if the cytogenetics/FISH results are 'normal' at screening or at any point during the study, no further cytogenetic/FISH analysis is required, except at the Treatment Discontinuation Visit or at the time of relapse (whichever occurs first).
- ^u Bone marrow aspirate/biopsy, peripheral blood smear, cytogenetic testing, and an IWG response assessment will be measured at the Treatment Discontinuation Visit or at the time of suspected relapse (whichever occurs first). If clinically inappropriate per the treating site, the subject may have bone marrow evaluation omitted if peripheral blast results are collected.
- [REDACTED]
- [REDACTED]
- [REDACTED]
- [REDACTED]
- ^z Blood PK sampling time points are specified in Table 3. [REDACTED]

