6.20.4. Modified IWG Response

Modified International Working Group response (Appendix D) criteria will be used to assess activity at the completion of predefined treatment Cycles 1, 2, 3 and 4 and at the Treatment Discontinuation Visit or at the time of suspected relapse (whichever occurs first). An IWG response assessment will be performed whenever a bone marrow assessment is performed in order to confirm CR or CRi, PR, or treatment failure. For subjects who are assessed as having partial response, the IWG response will be repeated at Cycle 8 unless the subject goes to allogeneic HSCT, and at the Treatment Discontinuation Visit or at the time of suspected treatment failure (whichever occurs first).

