Grade 3 ALT/AST values that return to levels that meet initial eligibility criteria within 7 days of IP interruption do not require a dose reduction. These subjects may resume treatment at the original dose level. If the toxicity recurs, then dose de-escalation is indicated.

Day 1 of Cycle 2 and beyond may be delayed up to 14 days from the end of the prior cycle in order for subjects to recover from toxicity. If a study interruption has lasted for more than 14 days, the Investigator should contact the Medical Monitor to discuss whether the subject should be continued on the study.

Special Instructions for Myelosuppression:

Due to the underlying marrow infiltrating malignancy, myelosuppression is universal and expected in patients with AML. Therefore, myelosuppression (anemia, neutropenia, and thrombocytopenia) will not require dose reduction or interruption *except* in the case of neutropenia or thrombocytopenia due to prolonged bone marrow aplasia at the end of a treatment cycle in subjects who have achieved remission.

- For subjects who have achieved remission:
 - Prolonged bone marrow aplasia is defined as lack of peripheral blood count recovery to $ANC \geq 500/mm^3$ and platelets $\geq 50,000/mL$ without transfusion for 7 days in the absence of leukemia (bone marrow biopsy demonstrate hypocellularity without evidence of leukemia) at Day 43 of a cycle (ie, failure to start the next cycle within 14 days).
 - The lenalidomide dose will be interrupted and the start of the next cycle will be delayed until count recovery.
 - Prolonged delay (ie, failure to start the next cycle within 14 days) for subjects in remission will require dose de-escalation.
 - If the peripheral blood counts recover within 14 days, the subject will proceed to the next cycle without dose reduction.

- If the peripheral blood counts do not recover within 14 days, repeat bone marrow evaluation including bone marrow biopsy every 7-14 days to assess cellularity and to evaluate for relapse/persistent leukemia.
- For subjects who have not achieved remission:
 - In general, subjects who have not achieved remission and have evidence of residual leukemia will proceed to the next cycle as scheduled regardless of count recovery.
- For subjects with residual leukemia:
 - If residual leukemia is demonstrated and the subject previously had achieved CR/CRi, the subject will be discontinued from the study.

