 - If residual leukemia is demonstrated, which is stable from prior assessments (ie, subject with previous PR/treatment failure), the subject will proceed to the next cycle of lenalidomide as scheduled without delay and without regard to peripheral blood counts. Lenalidomide dose will NOT be decreased.

Special Instructions for Management of Graft Versus Host Disease (GVHD):

Post-HSCT subjects will be monitored closely for development of GVHD of the skin, liver, or gut, see [Appendix K](#) for grading criteria.

- Subjects with Grade 1 or 2 GVHD (any site, biopsy proven or probable, ie, requires systemic steroid treatment) will be managed at the discretion of the local bone marrow transplant (BMT) physician and lenalidomide will be held.
 - If the acute GVHD resolves within 14 days and the subject is being treated with no more than topical therapies and/or up to 0.5 mg/kg/day corticosteroids (prednisone equivalents), lenalidomide will be restarted at the same prior dose.
 - After 14 days, subjects requiring more than 0.5 mg/kg/day corticosteroids or other systemic therapy (ie, not including topical therapies) to manage the acute GVHD will be discontinued from the study.
- Subjects with Grade 3 or 4 GVHD (any site, suspected or biopsy proven) will have lenalidomide discontinued permanently and will be managed at the discretion of the local HSCT physician. These subjects will be discontinued from the study.

Guidelines for Renal Insufficiency

- Lenalidomide is primarily excreted unchanged by the kidney; therefore, study treatment will be held for subjects who experience CLcr < 70 mL/min (confirmed by repeat creatinine measurement within 3 days). If CLcr returns to levels that meet initial eligibility criteria (> 70 mL/min) within 7 days of IP interruption, the subject may resume treatment at a full dose. However, if the subject improves within 14 days, a dose reduction by 1 dose level of study treatment will be considered at the discretion of the Investigator, and after careful consideration of the subject's renal impairment etiology and the subject's tolerability to lenalidomide. If toxicity does not resolve to eligibility by 14 days of dose interruption, then the subject will be off study treatment.

Dose Discontinuation:

- Subjects experiencing a thromboembolic event unrelated to a central line will be discontinued from lenalidomide treatment.

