An external independent data monitoring committee (DMC) will evaluate safety and treatment efficacy data in an ongoing, periodic manner to assess benefit-to-risk considerations throughout the study. The function of the DMC is to monitor the safety and activity of the study treatment. After 4 subjects have completed at least 1 cycle of study treatment, the DMC will evaluate the safety data and provide a recommendation. The DMC will also provide recommendations about the continuation of the study from Stage 1 to Stage 2 (continue as planned, continue with modifications or stop treatment and/or enrollment) and advise on ways to improve quality. The DMC responsibilities, authorities, and procedures will be documented in the DMC charter, which will be endorsed by the DMC prior to the first data review meeting.

The study will consist of 3 phases: Screening Phase, Treatment Phase and Follow-up Phase.

The study will be conducted in compliance with International Conference on Harmonisation (ICH) Good Clinical Practices (GCPs).

Screening Phase

The Screening Phase will start from the time of signing the informed consent form (ICF)/informed assent form (IAF) and will last no more than 14 days, at which time the

Treatment Phase will begin (Cycle 1 Day 1). Subject's screening procedures are to occur during the Screening Phase within 14 days prior to dosing on Cycle 1 Day 1.

Treatment Phase

The lenalidomide dose will be calculated based on body weight. The starting dose will be 2 mg/kg/day with a maximum dose of 70 mg/day. Subjects enrolled in the study will receive lenalidomide for the first 21 days of each 28-day treatment cycle for up to a maximum of 12 cycles of study treatment. After the completion of 12 cycles of study treatment, subjects who demonstrate clinical benefit (CR/CRi/PR) or resistant disease as per the Investigator may continue to receive lenalidomide in an OEP until they meet the criteria for study discontinuation.

In the event of a specific protocol-defined toxicity, no more than 2 dose reductions will be allowed to doses of 1.4 mg/kg/day (not exceeding 50 mg/day) and 1 mg/kg/day (not exceeding 35 mg/day). The dose will not be re-escalated once it has been reduced. Subjects who do not tolerate the minimum dose level of 1 mg/kg/day (not exceeding 35 mg/day) will be discontinued from the study.

Follow-up Phase

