10.2.2. Overall Response Rate

Overall response rate defined as the proportion of subjects with best response (CR, CRi or PR) among all subjects in the ITT population (i.e. subject will be considered as having a response if they achieve at least PR). Subject achieving less than PR (i.e. 'treatment failure') or having no assessment will be considered as a non-responder. If a subject is missing some assessments, their best response from available assessments will be selected as the response. Responses occurring after a treatment failure will not be considered. All assessments collected while a subject is under study treatment (incorporating, wherever applicable, the 28 day rule, i.e. last dose plus 28 days) will be considered.

The ORR formula will be the following

$$\text{ORR} = (\text{number of CR, CRi or PR from start to the end of period under analysis}) / (\text{number of subjects within the ITT population}).$$

The ORR rate at the end of Cycles 1, 2, 3, 4, 8 and 12 will be categorized, and the rate will be calculated for each cycle dividing the number of subjects with response in the cycle by the number of subjects entering the cycle. The formula will be the following

$$\text{ORR cycle}_i = (\text{number of CR, CRi or PR from start of Cycle } i \text{ to the end of Cycle } i) / (\text{number of subjects entering Cycle } i \text{ within the ITT population}).$$

Proportions will be presented as percentages with frequency counts together with the Clopper-Pearson 95% CI, at the end of each pre-specified cycle.

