10.2.3. Disease Assessment Outcome

Disease assessment outcome (DAO) at the end of Cycles 1, 2, 3, 4, 8 and 12 of lenalidomide administration shall be categorized according to the Cheson criteria (Cheson, 2003, see Section 18.1) into the following categories: CR, CRi, PR, Treatment Failure (Resistant Disease, Aplasia, Indeterminate Cause, Relapse after CR or CRi, Molecular or Cytogenetic relapse), Missing/not done. Responses occurring after a treatment failure will not be considered. The DAO rate for each of the response criteria will be calculated as the total number of subjects in a given response category at each time point over the number of subjects entering each corresponding cycle. The formula will be the following:

DAO category cycle_i = (number of subjects with DAO category from start of Cycle i Day 1 to the end of Cycle i) / (number of subjects entering Cycle i within the ITT population)*100.

Proportions will be presented as percentages with frequency counts together with the Clopper-Pearson 95% CI, per response category at the end of each pre-specified cycle.

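### The SAP discards any CR/CRi that follows a treatment failure outcome, yet stable resistant disease at an early on-treatment marrow is itself graded treatment failure, so late responders within Cycles 1–4 are lost from the primary endpoint

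*SAP*

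**What the plan says.** SAP Section 10.1 defines the primary endpoint as CR or CRi, assessed locally, at the end of Cycle 1, 2, 3 or 4. The response need not persist to Cycle 4. The paragraph then adds: "Responses occurring after a treatment failure assessment outcome will not be considered". Protocol Section 10.6.1 defines the same endpoint without that sentence.

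The passages that determine what counts as a treatment failure outcome are:

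- **When response is graded.** Protocol Table 2, note r: "An IWG response assessment will be performed whenever a bone marrow assessment is performed". Marrows are due on Days 22–27 of each of Cycles 1 to 4. Only the Cycle 3 marrow may be skipped, and only after a CR/CRi in the first two cycles.
- **What the grades are.** Protocol Section 6.20.4: "IWG response assessment will be performed whenever a bone marrow assessment is performed in order to confirm CR or CRi, PR, or treatment failure". SAP Section 10.2.3 uses this list at the end of Cycles 1, 2, 3, 4, 8 and 12: "CR, CRi, PR, Treatment Failure (Resistant Disease, Aplasia, Indeterminate Cause, Relapse after CR or CRi, Molecular or Cytogenetic relapse), Missing/not done".
- **What lies below PR.** SAP Section 10.2.2: "Subject achieving less than PR (i.e. 'treatment failure') or having no assessment will be considered as a non-responder". The criteria table in SAP Section 18.1 describes resistant disease as stable persistent AML without CR, CRi or PR.
- **What happens to these subjects.** Protocol Section 8.2.1 says that, in general, "subjects who have not achieved remission and have evidence of residual leukemia will proceed to the next cycle as scheduled". Of stable residual leukemia it says "ie, subject with previous PR/treatment failure), the subject will proceed to the next cycle of lenalidomide as scheduled".

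SAP Sections 10.2.2 and 10.2.3 repeat the exclusion for overall response rate (ORR) and disease assessment outcome.

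**The concern.** A rule that ignores responses after treatment failure is sensible if failure means progression or the end of treatment. Here the category also holds the ordinary early state of a subject who has not yet responded but stays on drug. Read as written, the sentence turns a four-cycle response window into one that closes at the first marrow graded below PR.

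The primary estimand then differs from the protocol's, and SAP Section 16 does not say so. That section records only that treatment failure replaced progressive disease in the response criteria. This may be where the rule came from, but that is inference.

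The error runs one way: it can remove responders and never adds any. At exactly 3 of 18 or 8 of 43 true responders, one excluded subject reverses the decision. The SAP is also uneven internally. Time to response (Section 10.2.1) carries no such exclusion, so one subject could have a time to response yet be a non-responder for the primary endpoint and ORR.

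**Working it through.** **Step 1: does the rule reach on-treatment stable disease?** Take a subject with persistent AML, not in PR, at the Cycle 1 marrow.

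- Protocol 6.20.4 requires a grade, and the only grade available below PR is treatment failure.
- SAP 10.2.3 assigns it at the end of Cycle 1 as resistant disease.
- Protocol 8.2.1 sends the subject to Cycle 2.
- If the Cycle 3 marrow shows CR, protocol 10.6.1 counts it and SAP 10.1 does not.

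A late response is counted only if every earlier assessment was PR or missing. PR is a narrow route. It requires ANC and platelet recovery, so falling blasts with cytopenia still grade below PR. It also requires 5–25% marrow blasts and at least a 50% fall. Entry needs only ≥5% blasts, and a subject entering below 10% would fall below 5% on halving, so cannot be graded PR.

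**Step 2: reproduce the plan's design.** Inputs from protocol 10.3 and SAP 4.4: p0 = 0.10, p1 = 0.25, n1 = 18, n2 = 25, continue if at least 3/18 respond, conclude activity if at least 8/43 respond.

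P(go | p) = Σ over x = 3..18 of Bin(x; 18, p) × P[Bin(25, p) ≥ 8 − x]

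P(Stage 1 stop | p) = P[Bin(18, p) ≤ 2]

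- At p = 0.10: P(go) = 0.0480, early stop 0.734, expected N = 18 + 25 × (1 − 0.734) = 24.7.
- At p = 0.25: P(go) = 0.8003; early stop = 0.0056 + 0.0338 + 0.0958 = 0.135.

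This matches the stated 5% level and 80% power. A grid search for the optimal design under these constraints returns the same 18/43 design.

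**Step 3: apply the exclusion.** Let e be the share of true responders with a treatment failure marrow before their first CR/CRi. The documents do not give e; it is an assumption shown as a range. The countable rate is p × (1 − e). Because counted responders cannot exceed true ones, the chance of stopping despite at least 3 true responders in 18 is the Stage 1 stop probability minus 0.1353.

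| e | Countable rate (true 25%) | Power | Stage 1 stop | Stop despite ≥3 true in 18 | Expected counted in 43 | Type I error (true 10%) |
|---|---|---|---|---|---|---|
| 0 | 25.0% | 80.0% | 13.5% | 0 | 10.8 | 4.8% |
| 10% | 22.5% | 69.7% | 19.5% | 5.9% | 9.7 | 2.8% |
| 25% | 18.75% | 48.9% | 31.7% | 18.1% | 8.1 | 1.1% |
| 50% | 12.5% | 13.1% | 60.5% | 47.0% | 5.4 | 0.1% |

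Solving P(go) = 0.50 gives e = 0.243. At e = 60% the countable rate is 0.25 × 0.40 = 0.10, the null rate.

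**Step 4: is e likely to be near zero?** The documents cannot settle this. Protocol Section 1.4.1 cites an adult monotherapy study with median time to CR/CRi of 30 days (range 1 to 72). That median falls after the Day 22–27 Cycle 1 marrow. Those patients were newly diagnosed and elderly, and their earlier marrow grades are not reported, so this is context and not an estimate of e.

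**The case against.** The strongest counter-case is a narrower reading, in which treatment failure means worsening or the end of treatment. Some passages use it that way: PR subjects have a repeat marrow at suspected treatment failure, SAP 10.2.4 measures a durable response up to treatment failure, and SAP 5.3.2 takes treatment failure from the treatment disposition page. The term also replaced progressive disease. The definition's post-therapy wording could be read as after drug is stopped.

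This does not carry. SAP 10.1 speaks of an assessment outcome and takes response from the IWG eCRF page. SAP 5.3.2 uses the disposition page only where no assessment could be made. SAP 10.2.3 lists resistant disease as an outcome at each cycle end, and protocol 8.2.1 describes continuing subjects with previous treatment failure.

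Some supports are weaker than others. SAP 4.1 says "subjects who demonstrate clinical benefit (CR/CRi/PR) or resistant disease as per the Investigator may continue to receive lenalidomide in an OEP", which shows resistant disease as an on-treatment status. But the current protocol says only clinical benefit, and the amendment log deletes the term, so this may be carry-over. SAP 10.2.2 defines less than PR for best response, not for each marrow. Silence in SAP 10.2.1 is an inconsistency, not proof. The conclusion does not need these.

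SAP 14 states the Stage 1 decision as a count of CR/CRi without repeating the exclusion. It does, however, report the same four-cycle rate that Section 10.1 defines, and gives no other derivation.

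Three limits stand. The size depends wholly on e. The bias is conservative for false positives. The realised effect may be small: SAP Section 16 drops some analyses, including durable response, because of low numbers or redundancy. None of these cures an undeclared change to the primary endpoint.

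**Conclusion.** The concern holds and must be fixed. As written, SAP 10.1 removes late CR/CRi that protocol 10.6.1 counts, and the SAP does not declare the departure. The direction is certain: the response rate, the Stage 1 decision and the final decision can only be pushed downward. The size is conditional on the assumed share of responders with an earlier marrow below PR: at a true rate of 25%, a 10% share costs about 10 points of power, and a share of about 24% brings power to 50%. Confidence is high on the wording conflict and on the arithmetic given e. The documents support no single value of e.

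**What to change.** - **Main change.** In SAP 10.1, 10.2.2 and 10.2.3, state that a resistant-disease outcome at an earlier on-treatment assessment does not preclude a later CR/CRi (or PR, for ORR).
- **If an exclusion is kept.** Limit it to responses first observed after the start of new anticancer therapy or HSCT. The protocol's endpoint section does not contain that rule either, so declare it in SAP Section 16.
- **Consistency.** In SAP 10.2.4, let a first CR/CRi after an earlier PR or resistant disease qualify, while a response regained after loss of CR/CRi remains not durable. Section 16 drops that summary, so this is secondary.
- **Separate and minor.** Clarify how the ANC and platelet lines of the CRi row combine, so that a marrow below 5% blasts with one unrecovered lineage is clearly classified. The main point does not depend on this.

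**Cost.** The main change is SAP wording plus a re-run of the response derivation on IWG data already collected. It needs no new subjects or assessments. The CRi clarification touches protocol Appendix D, so it would need an amendment under protocol Section 14.5 and a check of local classifications already made.
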